6.1.7 Adverse Events Associated with Commercial Drug

In a study of 989 patients given a rapid IV push of 100 mg IV thiamine, the only identified side effects were immediate, transient burning (1.02%) and generalized pruritis (0.093%).²⁷ Anaphylaxis has been reported at a rate of one reaction per every 5 million ampules used.²⁸ The following have also been reported with unknown frequency: a feeling of warmth, weakness, sweating, nausea, restlessness, tightness of the throat, angioneurotic edema, cyanosis, pulmonary edema, and hemorrhage into the gastrointestinal tract. Parenteral doses of 100 to 500 mg singly have been administered without adverse effect.²⁹ A comprehensive list of adverse effects can be found at the following web address: http://editor.fresenius-kabi.us/Pis/Thiamine_Inj_45819E_May_08.pdf

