7.11 Assessment of Efficacy

In order to be considered evaluable for efficacy, patients must:

- receive all 7 days of the treatment; a patient must receive at least 17/21 (80%) thiamine doses
- have delirium assessed at least weekly until one of the following is met:
 1. The participant is found to be delirious (DRS>12)
 2. The participant is at least 30 days post-transplant
 3. The participant is discharged

If a patient is deemed not evaluable, they will be replaced by a new patient. However, if a patient develops delirium during the intervention, they will still

receive the full 7 day course, not be replaced, and included in the efficacy analysis.

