8.5 Data and Safety Monitoring Plan

This is a Phase II, single site study of 60 individuals to gather preliminary data on the efficacy and safety of high dose IV thiamine for delirium prevention in patients undergoing HSCT. We will follow our standard protocol for monitoring of clinical trials. Subjects are screened to ensure that there are no contraindications to their participation.

The study Co-PIs, Drs. [name] and [name], will be responsible for continuous monitoring of patient safety during the trial. For non-serious Adverse Events (AEs), documentation will begin from the first day of study treatment and continue through the 30 day follow-up period after treatment is discontinued. Collected information will be recorded in Case Report Forms (CRF) for that patient. A description of the event, its

severity or toxicity grade, onset and resolved dates (if applicable), and the relationship to the study drug will be included. For any experience or condition that meets the definition of a serious adverse event (SAE), recording of the event will begin after signing of the informed consent and continue through the 30 day follow-up period after treatment is discontinued. These events will be recorded in the CRF for that patient within 24 hours of learning of its occurrence. If the event is both serious AND unexpected, it will also be recorded on the MedWatch Form 3500A, as per 21 CFR 312.32, and forwarded to the FDA in accordance with 21 CFR 314.80 (for marketed drugs). The UNC IRB will be notified of all SAEs that qualify as an Unanticipated Problem (serious, unexpected, and related) as per the UNC IRB policies. In accordance with these policies, an aggregated list of all SAEs will be submitted to the UNC IRB annually at the time of study renewal.

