9.0 STATISTICAL CONSIDERATIONS

9.1 Study Design/Study Endpoints

This is a randomized double-blind controlled trial in participants undergoing allogeneic hematopoietic stem cell transplantation (HSCT) to evaluate if high dose intravenous (IV) thiamine can prevent delirium and minimize the deleterious impact of delirium on health-related quality of life (HRQOL), functional status, and other neuropsychiatric outcomes. We will recruit 60 evaluable patients scheduled for allogeneic HSCT at UNC, randomize them to treatment with high

dose IV thiamine (n = 30) versus placebo (n = 30), and systematically evaluate all participants for delirium and related comorbidities.

Analysis Populations: The Safety Population will be defined as all subjects who were enrolled and received at least one dose of study medication. Efficacy Evaluable Population will be defined as all subjects who received at least 80% (17/21) of total possible intervention doses and participated in at least one delirium assessment weekly.

The primary efficacy endpoint is delirium incidence defined as DRS >12. Secondary endpoints include delirium duration and severity, along with FACT-BMT, PROMIS-D, PTSS-14, ECOG-PS, and MOCA.

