9.3 Data Analysis Plans

To compare delirium incidence, severity, and duration between recipients of high dose IV thiamine and placebo during hospitalization for HSCT. The primary outcome measure is delirium incidence, defined as: DRS > 12. Secondary outcomes are differences in delirium duration (in days) and delirium severity, in which higher DRS scores suggest more severe delirium. A two group chi-squared test will be used to compare rates of delirium in the intervention and control group. Maximum severity score will be analyzed using two group t-tests, and time to delirium will be compared between groups using the Kaplan-Meier

method. For those with delirium, two group t-tests will compare the duration of delirium between intervention groups; Kaplan-Meier methods may also be considered for time to delirium resolution.

To determine if thiamine status is predictive of future delirium onset. We will examine the relationship between thiamine levels at the end of the seven day administration of thiamine and the development of delirium at any point during the thirty days post-transplant or the post-transplant hospitalization, whichever comes first. Patients who develop delirium prior to the end of the thiamine treatment will not be included in this analysis. We will examine the sensitivity and specificity of this relationship with ROC curves, and attempt to find a cutoff for thiamine levels that is associated with the development of delirium.

To investigate the effects of high dose IV thiamine on long-term health-related quality of life (HRQOL), functional status, depression, post-traumatic stress symptoms, and cognitive functioning in patients hospitalized for HSCT. Scores on FACT-BMT, PROMIS-D, PTSS-14, ECOG-PS and MOCA will be compared between intervention and control groups. We will summarize scores on the FACT-BMT, PROMIS-D, PTSS-14, ECOG-PS, and MOCA between the intervention and control groups at one, three, and six months post-transplant. Longitudinal modeling will be performed to examine differences/changes over time.

Safety Analyses: We will tabulate AEs and SAEs, by treatment and placebo, within strata. We will include all AEs which occurred at a rate of more than 5% in any treatment.

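### The 5% cut in Section 9.3 leaves any non-serious AE seen in at most one patient per arm out of the planned final safety table

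*Combined protocol and SAP*

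**What the plan says.** Section 9.3 (Safety Analyses) has two sentences. The first is "We will tabulate AEs and SAEs, by treatment and placebo, within strata". The second is "We will include all AEs which occurred at a rate of more than 5% in any treatment". No exemption is given for suspected drug reactions, for grade 3 or higher events, or for the events named in the Section 5.3 toxicity table (anaphylaxis, infusion site extravasation, pruritus). No complete AE listing is planned for the final analysis.

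The denominator comes from Section 9.1, which plans 30 evaluable patients per arm and states: "The Safety Population will be defined as all subjects who were enrolled and received at least one dose of study medication". Section 7.11 adds: "If a patient is deemed not evaluable, they will be replaced by a new patient". The safety arms can therefore exceed 30.

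Section 6.1.7 gives the expected reactions. Among 989 patients given one rapid 100 mg push, burning occurred in 1.02% and generalized pruritus in 0.093%. Other reactions, including angioneurotic edema, are listed with unknown frequency. Section 8.5 describes the trial as one to "gather preliminary data on the efficacy and safety of high dose IV thiamine".

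**The concern.** A percentage cut is usually meant to shorten a table in a large trial, where 5% is many patients. Here it falls between one and two patients, so it acts as a rule against single cases.

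That sits badly with the protocol's own approach to causality. Section 8.1.2 counts a single occurrence of an uncommon event strongly tied to drug exposure as evidence for a drug cause, and uses angioedema as an example. It also counts an aggregate comparison of specific events between groups. A non-serious event of the first kind is what the rule removes, and a filtered table weakens the second.

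Section 1.4 says thiamine has not been studied specifically in HSCT patients and that rates for its rarer side effects are not available. A reader of the final report could not tell whether an expected mild reaction never occurred or occurred once in an arm and was filtered out.

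**Working it through.** **1. The plan's own arm size.** Inputs from Section 9.2: proportions 0.445 and 0.155, one-sided 0.05, 30 per arm. With pooled variance and no continuity correction, the mean proportion is 0.30 and

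z = [0.29 × √30 − 1.645 × √(2 × 0.30 × 0.70)] / √(0.445 × 0.555 + 0.155 × 0.845) = (1.588 − 1.066) / 0.615 = 0.85,

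which gives power of 80.2%. The odds ratio is (0.155/0.845) / (0.445/0.555) = 0.229. Both agree with the plan, so 30 per arm is the right starting denominator.

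**2. Cases needed to pass the cut.** The rule is strict (more than 5%), so an arm of n needs the smallest k with k/n > 0.05.

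| Dosed in arm | One case | Two cases | Cases needed |
|---|---|---|---|
| 20 | 5.00% | 10.00% | 2 |
| 30 | 3.33% | 6.67% | 2 |
| 39 | 2.56% | 5.13% | 2 |
| 40 | 2.50% | 5.00% | 3 |

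A single case fails in any arm of 20 or more. Replacement of non-evaluable patients does not help: once an arm reaches 40 dosed, two cases fail as well.

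**3. How often a reaction that is seen would be left out.** Let q be the risk per thiamine patient over the course, with n = 30 and patients independent:

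- P(seen) = 1 − (1 − q)^30
- P(exactly one) = 30 q (1 − q)^29
- P(kept) = P(seen) − P(exactly one)
- share left out when seen = P(exactly one) / P(seen)

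This assumes that placebo contributes at most one case; two placebo cases would keep the row.

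Section 6.1.7 reports single pushes. Section 5.2 gives three 30-minute infusions a day for seven days, or 21 doses. The cited rate can be read in two ways. Either it is the whole-course risk, q = p, or it applies independently to each dose, q = 1 − (1 − p)^21. Both are assumptions.

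Worked case, burning with q = 0.0102: P(seen) = 1 − 0.9898^30 = 26.5%. P(exactly one) = 30 × 0.0102 × 0.9898^29 = 22.7%. P(kept) = 3.7%. Share left out = 22.7/26.5 = 86%.

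| Reaction and reading | q | P(seen) | P(kept) | Left out when seen |
|---|---|---|---|---|
| Burning, whole course | 1.02% | 26.5% | 3.7% | 86% |
| Burning, per dose | 19.4% | 99.8% | 98.7% | 1.1% |
| Pruritus, whole course | 0.093% | 2.8% | 0.04% | 99% |
| Pruritus, per dose | 1.93% | 44.4% | 11.4% | 74% |
| Illustrative | 2% | 45.5% | 12.1% | 73% |
| Illustrative | 3.3% | 63.5% | 26.0% | 59% |

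The pruritus rate is itself poorly known: 0.00093 × 989 = 0.92, about one case.

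**4. Effect of removing the cut.** A reaction then appears whenever it is seen. On the whole-course reading, the chance that burning appears in the thiamine column rises from 3.7% to 26.5%, and for pruritus from 0.04% to 2.8%.

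**5. Denominator.** Section 9.3 tabulates within strata, and Section 7.3 defines 2 × 2 = 4 of them. If the rate were taken within an arm-by-stratum cell averaging 30/4 = 7.5 patients, one case would be 1/7.5 = 13% and would be kept. The words about any treatment favour the whole arm, but the plan does not say so.

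**The case against.** Several points on the other side stand.

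- **Not every single-patient AE is dropped.** SAEs are to be tabulated, and the 5% sentence names only AEs. An AE seen once on thiamine and twice on placebo passes, with its whole row.
- **The data and the oversight are intact.** Sections 8.2 and 8.5 put AEs on the CRF with grade, dates and relationship. Section 8.5 sends grade 3 or higher AEs to the DSMC with no frequency cut. A reader might infer that isolated grade 3 reactions escape review, but the documents say otherwise. What such a non-serious event lacks is an assured place in the final table.
- **The 86% is not a robust headline.** It treats a single-push rate as the risk over up to 21 slower infusions. On the per-dose reading, burning is almost always kept.
- **One case carries little information on rate.** For 1/30 the exact 95% interval runs from 0.08% to 17.2%. Safety is also not among the objectives or endpoints in Sections 2 and 3; it appears as an aim in Section 8.5. A reader might infer that the rule hides most of the drug-related signal, but nothing in the documents supports that.
- **The sentence is worded as inclusion.** It might describe a summary table only. That is possible, but nothing says so and no fuller table is planned. Read plainly, it is a filter.

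These points narrow the scope. None of them gives a single non-serious reaction a place in the planned final table.

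**Conclusion.** The point holds in limited form. If the rule is read as a filter with the treatment arm as denominator, a non-serious AE with at most one case in each arm is left out at about 30 per arm. In an arm of 40 or somewhat more, two cases do not pass either. This rests only on the stated rule and the planned arm size, not on any reaction rate.

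The share of known reactions left out when seen does depend on an assumed rate and on independence between patients (and between doses, on the per-dose reading). For burning it runs from about 86% to about 1%, so no single figure should be quoted. For pruritus it is high on both readings, about 99% and 74%, although few cases are expected: 30 × 0.00093 = 0.03, or 30 × 0.0193 = 0.58.

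The shortfall is in the final safety table of a trial that says it gathers preliminary safety data. It is worth correcting because the stated rule gives a less complete report than the data already collected would allow.

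**What to change.** Replace the second safety sentence in Section 9.3 with a plan that does the following:

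- Tabulates or lists all AEs by term, grade, relationship to study drug and arm, for the Safety Population, with no frequency threshold.
- States that SAEs are shown in full whatever their frequency.
- Keeps the cut of more than 5% only for a short summary table, labelled as such.
- Defines the rate for that summary as patients with the event divided by the safety population in the same arm, and says how the display within strata relates to it.

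No new data, visits or patients are needed, because Section 8.2 already collects description, grade, dates and relationship. The downside is a longer table with many single-patient rows, which the short summary table offsets.

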10.0 STUDY MANAGEMENT

10.1 Institutional Review Board (IRB) Approval and Consent

It is expected that the IRB will have the proper representation and function in accordance with federally mandated regulations. The IRB should approve the consent form and protocol.

In obtaining and documenting informed consent, the investigator should comply with the applicable regulatory requirement(s), and should adhere to Good Clinical Practice (GCP) and to ethical principles that have their origin in the Declaration of Helsinki.

Before recruitment and enrollment onto this study, the patient will be given a full explanation of the study and will be given the opportunity to review the consent form. Each consent form must include all the relevant elements currently required by the FDA Regulations and local or state regulations. Once this essential information has been provided to the patient and the investigator is assured that

the patient understands the implications of participating in the study, the patient will be asked to give consent to participate in the study by signing an IRB-approved consent form.

Prior to a patient's participation in the trial, the written informed consent form should be signed and personally dated by the patient and by the person who conducted the informed consent discussion.

10.2 Required Documentation

Before the study can be initiated at any site, the following documentation must be provided to the Clinical Protocol Office (CPO) at the University of North Carolina.

- A copy of the official IRB approval letter for the protocol and informed consent
- IRB membership list
- CVs and medical licensure for the principal investigator and any sub-investigators who will be involved in the study.
- The Investigator's signature documenting understanding of the protocol and providing commitment that this trial will be conducted according to all stipulations of the protocol is sufficient to ensure compliance
- CAP and CLIA Laboratory certification numbers and institution lab normal values
- Executed clinical research contract

10.3 Registration Procedures

All patients must be registered with the CPO at the University of North Carolina before enrollment to study. Prior to registration, eligibility criteria must be confirmed with the UNC Study Coordinator. To register a patient call the CPO at [[contact]]([contact]) Monday-Friday 9:00 am – 5:00 pm EST or email the UNC Project Manager.

10.4 Data Management and Monitoring/Auditing

The CPO of the UNC LCCC will serve as the coordinating center for this trial. Data will be collected through a web based clinical research platform, OnCore[®]. All data will be collected and entered into OnCore[®] by research coordinators from UNC LCCC.

The sponsor will provide direct access to source data/documents for trial-related monitoring, audits, IRB/IEC review, and regulatory inspection. As an investigator initiated study, this trial will also be audited by the LCCC compliance committee every six or twelve months.

10.5 Adherence to the Protocol

Except for an emergency situation in which proper care for the protection, safety, and well-being of the study patient requires alternative treatment, the study shall be conducted exactly as described in the approved protocol.

10.5.1 Emergency Modifications

UNC investigators may implement a deviation from, or a change of, the protocol to eliminate an immediate hazard(s) to trial subjects without prior UNC IRB approval.

For any such emergency modification implemented, a UNC IRB modification form must be completed by UNC Research Personnel within five (5) business days of making the change.

10.5.2 Single Patient/Subject Exceptions

Any request to enroll a single subject who does not meet all the eligibility criteria of this study requires the approval of the UNC Principal Investigator and the UNC IRB.

10.5.3 Other Protocol Deviations/Violations

According to UNC's IRB, a protocol deviation is any unplanned variance from an IRB approved protocol that:

- Is generally noted or recognized after it occurs
- Has no substantive effect on the risks to research participants
- Has no substantive effect on the scientific integrity of the research plan or the value of the data collected
- Did not result from willful or knowing misconduct on the part of the investigator(s).

An unplanned protocol variance is considered a violation if the variance meets any of the following criteria:

- Has harmed or increased the risk of harm to one or more research participants.
- Has damaged the scientific integrity of the data collected for the study.
- Results from willful or knowing misconduct on the part of the investigator(s).
- Demonstrates serious or continuing noncompliance with federal regulations, State laws, or University policies.

If a deviation or violation occurs please follow the guidelines below:

Protocol Deviations: UNC or Affiliate personnel will record the deviation in OnCore[®], and report to any sponsor or data and safety monitoring committee in accordance with their policies. Deviations should be summarized and reported to the IRB at the time of continuing review.

Protocol Violations: Violations should be reported by UNC personnel within one (1) week of the investigator becoming aware of the event using the same IRB online mechanism used to report Unanticipated Problems.

Unanticipated Problems: Any events that meet the criteria for “Unanticipated Problems” as defined by UNC’s IRB must be reported by the study personnel using the IRB’s web-based reporting system.

10.6 Amendments to the Protocol

Should amendments to the protocol be required, the amendments will be originated and documented by the Principal Investigator at UNC. It should also be noted that when an amendment to the protocol substantially alters the study design or the potential risk to the patient, a revised consent form might be required.

The written amendment, and if required the amended consent form, must be sent to UNC’s IRB for approval prior to implementation.

10.7 Record Retention

Study documentation includes all eCRFs, data correction forms or queries, source documents, Sponsor correspondence to Investigators, monitoring logs/letters, and regulatory documents (e.g., protocol and amendments, IRB correspondence and approval, signed patient consent forms).

Source documents include all recordings of observations or notations of clinical activities and all reports and records necessary for the evaluation and reconstruction of the clinical research study.

Government agency regulations and directives require that all study documentation pertaining to the conduct of a clinical trial must be retained by the study investigator. In the case of a study with a drug seeking regulatory approval and marketing, these documents shall be retained for at least two years after the last approval of marketing application in an International Conference on Harmonization (ICH) region. In all other cases, study documents should be kept on file until three years after the completion and final study report of this investigational study.

10.8 Obligations of Investigators

The Principal Investigator is responsible for the conduct of the clinical trial at the site in accordance with Title 21 of the Code of Federal Regulations and/or the Declaration of Helsinki. The Principal Investigator is responsible for personally overseeing the treatment of all study patients. The Principal Investigator must assure that all study site personnel, including sub-investigators and other study

staff members, adhere to the study protocol and all FDA/GCP/NCI regulations and guidelines regarding clinical trials both during and after study completion.

The Principal Investigator will be responsible for assuring that all the required data will be collected and entered into the eCRFs. Periodically, monitoring visits will be conducted and the Principal Investigator will provide access to his/her original records to permit verification of proper entry of data. At the completion of the study, all eCRFs will be reviewed by the Principal Investigator and will require his/her final signature to verify the accuracy of the data.

12.0 APPENDICES

Appendix A: Suggested Management of Delirium

1. Obtain further laboratory work-up^{45,46}

In all patients with delirium the following should be considered:

- Blood chemistries: electrolytes, glucose, calcium, albumin, blood urea nitrogen (BUN), creatinine, AST, ALT, bilirubin, alkaline phosphatase, magnesium, phosphorus
- Complete blood count (CBC)
- Electrocardiogram
- Chest X-ray
- Measurement of arterial blood gases or oxygen saturation
- Urinalysis

In patients with delirium the following should be considered if felt to be clinically indicated:

- Urine culture and sensitivity
- Urine drug screen
- Blood cultures
- Measurement of serum levels of medications (e.g., tacrolimus, cyclosporine, etc.)
- Lumbar puncture
- Brain computerized tomography (CT) or magnetic resonance imaging (MRI)
- Electroencephalogram (EEG)
- Folate, B12

2. Treat any reversible abnormalities identified in work-up

3. Initiate environmental and supportive interventions

- Staff to open blinds every morning.
- Glasses, hearing aide, and patient's own shoes to bedside. Make available to patients when possible and encourage use.
- Encourage po fluids when appropriate, keep fluids within reach.
- Out of bed to chair with meals.
- Staff to assess orientation to person, time and place every morning and as needed throughout the day.
- Recommend extended visitation hours with familiar family/friends as feasible.
- Staff to minimize disturbances at night. Turn off television when patient asleep or when not in use.

4. Consult Psychiatry for a.) behavioral disturbance and/or b.) Delirium Rating Score > 12

Note: With the exception of urgent psychiatric consults needed overnight, on weekends, or on holidays, consultants will be limited to study investigators Drs. [name] and [name].

